### PROTOCOL AMENDMENT SUMMARY OF CHANGES

# **Amendment 3 (27 Jul 2022)**

This amendment is considered to be substantial based on the criteria set forth in Article 10(a) of Directive 2001/20/EC of the European Parliament and the Council of the European Union and any applicable local regulations.

#### **Overall Rationale for the Amendment**

The main reason for this amendment is to have all participants return on Day 75 for the EOS visit (instead of Day 43), regardless of ADA results, to maintain blinding of Alexion staff, the Investigator, and site staff. Changes implemented in Administrative Change Letter No.2 (14 Jun 2022), as well as some clarifications to wording and minor administrative changes, have also been made.

Changes to the protocol are detailed below:

Section Number and Name	Description of Change	Brief Rationale and/or Clarification
1.1 Synopsis	Text in the "Study Cohort and Duration" subsection was updated to reflect the Dosing and Follow-up Period as a total of 74 days for all participants.	To ensure consistency with the changes made to Schedule of Activities for EOS visit.
1.2 Schema, Figure 1	Number of days for Follow-up period was updated from 42 days to 74 days.	Number of days for the Follow-up period was updated to align with the EOS visit.
1.3 Schedule of Activities	Text was updated to reflect the change in Schedule of Activities from "Day 6 through Day 43" to "Day 6 through Day 75".	To ensure consistency with Table 3 in Schedule of Activities.
1.3 Schedule of Activities, Table 3 Footnote b	Title of Table 3 was changed from "Schedule of Activities – Single Ascending Dose Cohorts (Day 6 through Day 43 [or Day 75 if Positive for ADAs])" to "Schedule of Activities – Single Ascending Dose Cohorts (Day 6 through Day 75)" Footnote b text changed to reflect End of Study procedures will be performed on Day 75.	To maintain blinding of Alexion staff, the Investigator, and site staff, all participants are required to return on Day 75 for the EOS visit (instead of Day 43), regardless of ADA results.
2.4.1.1 Coronavirus Disease 2019	Removed text saying that Day 75 is only necessary for positive ADAs.	To ensure consistency with study timeline specified in Schedule of Activities.
4.5 Duration of Treatment and End of Study Duration	Text updated to specify that End of Study activities will occur on Day 75.	To clarify End of Study timeline for all participants.
4.5 Duration of Treatment and End of Study Duration, Figure 2	Figure 2 was updated to reflect Day 75 as the EOS, and text regarding EOS for ADA positive participants was removed.	To indicate Day 75 as EOS visit for all participants, regardless of ADA results.

Section Number and Name	Description of Change	Brief Rationale and/or Clarification
6.3 Measures to Minimize Bias: Randomization and Blinding  8.3.1 Time Period and Frequency for Collecting AE and SAE Information	Text related to ALP data blinding was added.  Edited text to specify AEs and SAEs will be collected until Day 75.	To maintain blinding of Alexion staff, the Investigator, and site staff. To ensure AE and SAE collection procedures reflect the Schedule of Activities including Day 75 for all participants
8.9.1 ADA Variables	Added text that includes "Treatment-boosted ADA Responses" as part of ADA positive categorizations.	This ADA response category was missing in the previous version of the protocol.
10.1.1 Regulatory and Ethical Considerations 10.2 Clinical Laboratory Tests, Table 10	Removed repeated mention of European regulation 536/2014. Removed repeated mention of "urea" as a parameter of "clinical chemistry" assessments.	This regulation was erroneously mentioned twice in a sentence.  This parameter was erroneously mentioned twice.
Overall	Added "Serum or urine pregnancy test" as a parameter of "other screening tests" laboratory assessments.  Minor administrative changes.	To ensure consistency with the Schedule of Activities.  For clarity.

Abbreviations: ADA = antidrug antibodies; AE = adverse event; ALP = alkaline phosphatase; SAE = serious adverse event

#### 1. PROTOCOL SUMMARY

# 1.1. Synopsis

**Protocol Title:** A Phase 1, Randomized, Double-blind, Placebo-controlled, Single Ascending Dose Study of Subcutaneously and Intravenously Administered ALXN1910 in Healthy Adult Participants

**Short Title:** Safety and Tolerability, Pharmacokinetic, and Pharmacodynamic Study of ALXN1910 in Healthy Participants

#### Rationale:

To gain an understanding of the safety, tolerability, PK, PD, and immunogenicity of ALXN1910, an FIH SAD study in healthy adult participants is proposed. Cohorts of Japanese and non-Japanese participants will also be evaluated to enable comparison between these 2 populations.

## **Objectives and Endpoints**

Objectives	Endpoints
Primary	
To assess the safety and tolerability of ALXN1910	Incidence of TEAEs and TESAEs
Secondary	
To assess the PK of single ascending doses of ALXN1910	Serum ALXN1910 PK (activity) and PK parameters
To explore the PD effects of single ascending doses of ALXN1910	
 
Plasma concentrations of PPi, PLP, PL, and PA versus time profiles
 

To assess the immunogenicity of ALXN1910	Incidence and titers of treatment-emergent ADAs
To assess the absolute bioavailability of ALXN1910 SC	GMR of AUC values of SC versus IV from serum concentrations of ALXN1910
To compare the safety, tolerability, PK, and PD of ALXN1910 SC between Japanese and non-Japanese healthy participants	Quantitative assessment of safety/tolerability and PK/PD parameters between Japanese and non-Japanese participants

Abbreviations: ADA = antidrug antibody; AUC = area under the serum concentration-time curve; GMR = geometric mean ratio; IV = intravenous; PA = pyridoxic acid; PD = pharmacodynamics(s); PK = pharmacokinetic(s); PL = pyridoxal; PLP = pyridoxal-5'-phosphate; PPi = inorganic pyrophosphate; SC = subcutaneous; TEAE = treatment emergent adverse event; TESAE = treatment emergent serious adverse event

## **Overall Design**

This is a Phase 1, randomized, double-blind, placebo-controlled study designed to evaluate the safety, tolerability, PK, PD, and immunogenicity of SADs of ALXN1910 SC and a SAD of ALXN1910 IV in up to approximately 48 healthy adult participants across treatment cohorts (up to approximately 36 participants to receive ALXN1910 and up to approximately 12 participants to receive placebo). Of the 48 participants, 8 will be of Japanese descent, defined as those participants whose parents and grandparents are both Japanese and who have spent less than 10 years outside of Japan.

For this FIH study, 8 participants will be randomly assigned in a 3:1 ratio to treatment and placebo in each of the 6 cohorts with escalating doses of 5 mg IV (Cohort 1), 15 mg SC

(Cohort 2), 15 mg IV (Cohort 3) in parallel with 15 mg SC in Japanese participants (Cohort 4) and 45 mg SC (Cohort 5), followed by 135 mg SC (Cohort 6). The first 2 participants randomized to each cohort will be dosed as a sentinel pair, with 1 participant on active treatment and 1 participant on placebo. This dosing strategy is justified given the large exposure margins (approximately 15-fold at the highest planned single dose of 135 mg SC). At the discretion of the Investigator, up to 3 more participants will be dosed at least 48 hours (as anticipated tmax occurs prior to 48 hours postdose) after the dosing of the sentinel pair, followed by dosing of the remaining participants in the cohort no earlier than 72 hours after sentinel pair dosing, as long as no suspension/stopping criteria have been met. At no time will more than 4 participants per cohort be dosed in a given day.

Participants who meet the qualifications for the study based on screening will be admitted to the CRU the day prior to dosing (Day -1) to undergo Check-in assessments per the applicable SoA. Final determination of eligibility will be determined based on Check-in and predose procedures, and eligible participants will be randomized to ALXN1910 or placebo on Day 1 prior to dosing. There will be extensive PK/PD sampling during the first 24 hours after dosing. Safety assessments will be performed per the SoA.

**Safety Review Committee:** The blinded SRC, consisting of the Investigator, Medical Monitor, Drug Safety Physician, Study Statistician, and Clinical Pharmacologist will evaluate the available study data at prespecified time points for participant safety and make recommendations on dose escalation, dose modification, or termination of the study. Decisions to continue, modify (explore the dose cohort further), or escalate dosing will be made by the Investigator and/or SRC.

#### **Number of Participants:**

Up to approximately 48 participants will be randomized according to a randomization schedule generated prior to the start of the study.

#### **Study Cohort and Duration:**

The participants in each dose cohort will be randomized in a 3:1 ratio to receive ALXN1910 or placebo. Following a Screening Period of up to 28 days, there will be a Dosing and Follow up Period (single dose on Day 1 through the EOS Visit) of approximately 74 days.

Cohort a	Number of Participants (ALXN1910:Placebo)	Route of Administration	Dose	Number of Doses/Dose Interval
1	8 (3:1)	IV b	5 mg	Single dose
2	8 (3:1)	SC	15 mg	Single dose
3	8 (3:1)	IV b	15 mg	Single dose
4	8 (3:1) (Japanese participants)	SC	15 mg	Single dose
5	8 (3:1)	SC	45 mg	Single dose
6	8 (3.1)	SC	135 mg	Single dose

**Table 1: Planned ALXN1910-HV-101 Dosing Cohorts** 

[figure not shown]
Abbreviations: IV = intravenous; PK = pharmacokinetic; SC = subcutaneous; SRC = Safety Review Committee

<sup>a Cohort 3, Cohort 4, and Cohort 5 can be initiated in parallel after dose escalation decision following SRC review of Cohort 2 safety and PK data.

<sup>b Slow IV infusions (rate of infusion = 6 mL/h) using a controllable infusion pump. The pharmacy manual will include details regarding infusion rate and duration.

### 1.2. Schema

Figure 1: Study Design Schematic

# 1.3. Schedule of Activities

The SoAs for all cohorts from Screening through Day 5 and from Day 6 through Day 75 are presented in Table 2 and Table 3, respectively.

Table 2: Schedule of Activities – Single Ascending Dose Cohorts (Screening through Day 5)

Study Day a	Screen -ing	Day -1				Day 1				Da	y 2	Da	y 3	Da	y 4	Day 5
Assessments	D -29 to D-2	Admit	Pre- dose	0 h I/ SOI	30 min post I/SOI	2 h post I/SOI	4 h post I/SOI	8 h post I/SOI	12 h post I/SOI	24 h post I/ SOI	36 h post I/ SOI	48 h post I/ SOI	60 h post I/ SOI	72 h post I/ SOI	84 h post I/ SOI	96 h post I/SOI
Status (OP or CRU)	OP		•	•	•			(	CRU	•		•	•	•		
Admission		X														
Discharge																$X^b$
Informed consent c	X															
Inclusion/exclusion d	X	X														
Medical history e	X															
Demographics	X															
Height, weight, and BMI f	X	X														
Hepatitis B and C screen	X															
HIV (Types 1 and 2) screen	X															
Follicle-stimulating hormone g	X															
Urine alcohol test	X	X														
Urine drug screen	X	X														
Serum pregnancy test h	X															
Urine pregnancy test h		X														
Randomization i			X													
Study intervention administration (ALXN1910 or placebo)				X												
Injection/infusion site evaluation j				X			X			X		X		X		X
Physical examination	X	X														

**Table 2:** Schedule of Activities – Single Ascending Dose Cohorts (Screening through Day 5)

Study Day a	Screen	Day -1				Day 1				Da	ıy 2	Da	y 3	Da	y 4	Day 5
Assessments	-ing D -29 to D-2	Admit	Pre- dose	0 h I/ SOI	30 min post I/SOI	2 h post I/SOI	4 h post I/SOI	8 h post I/SOI	12 h post I/SOI	24 h post I/ SOI	36 h post I/ SOI	48 h post I/ SOI	60 h post I/ SOI	72 h post I/ SOI	84 h post I/ SOI	96 h post I/SOI
Status (OP or CRU)	OP			I	I.	I.		(	CRU	I		I	I	I		1
Brief physical examination k										X		X				X
Vital sign measurements 	X		X		X	X	X	X	X	X		X		X		X
ECG m	X		X		X	X	X	X	X	X	X	X		X		X
Chemistry n	X	X								X						X
Hematology n	X	X								X						X
Coagulation n	X	X								X						X
Urinalysis n	X	X								X						X
PK°			X		X	X	X	X	X	X		X		X		X
PD (PPi, PLP, PL, and PA)			X							X		X				X
Urine for calcium, phosphorus, and creatinine p			X							X		X				X
Immunogenicity samples q			X													
Hypersensitivity reactions r			←Monitor continuously after dose→													
Hypersensitivity reaction laboratory tests (tryptase & complement C5b-9)s			$X$ $\leftarrow$ See footnote $\rightarrow$													
Concomitant medications			←Monitor continuously (after ICF is signed at Screening)→													
Adverse events review and evaluation					←Mon	itor conti	nuously	(after IC	F is signe	d at Scr	eening)	→				

Note: When scheduled at the same timepoint, the triplicate ECG should be performed first, followed by vital sign measurements, and then PK/PD sampling.

- a Permissible windows for study assessments are described in the Windows Allowance Document.
- b Participants will be discharged from the CRU after completing all Day 5 assessments. Due to the time needed for turnaround of laboratory test results, discharge will actually occur on Day 6.
- c A signed and dated IEC-approved ICF must be obtained before any study-specific screening procedures are performed.
- d Recheck clinical status before randomization and/or dose of study intervention.
- e Including substance usage (drugs, alcohol, tobacco, and caffeine) and past/current medical conditions.
- f Height and BMI only at Screening.
- g Only female participants claiming postmenopausal status will have a follicle-stimulating hormone test to confirm postmenopausal status.
- h All female participants will have a pregnancy test (serum at Screening and urine on Day -1) to confirm the participant is not pregnant. Any female participant who becomes pregnant while participating in the study will be withdrawn.
- i Randomization will occur predose on Day 1.
- j Injection/infusion site evaluations will be performed within 15 minutes after I/SOI and ± 15 minutes at 4 and 24 hours post I/SOI. See Section 10.5 for additional details.
- k Brief physical examination to be conducted on Day 5 prior to discharge from the CRU.
- At Screening, supine and standing (orthostatic) blood pressures will be performed according to the CRU's typical procedure to exclude participants who are prone to orthostatic hypotension.
- m Each ECG timepoint during the study will be 12-lead and performed in triplicate sequentially within 5 minutes, at least 1 minute apart after 10 minutes of bedrest in supine position (note, no bedrest is required post ECG), at Screening and 90, 75, and 60 minutes before dosing. ECGs should not be performed within 1 hour after any major meal or major meals should be withheld until after ECG assessments.
- n Investigators should review Day 5 laboratory results to ensure each participant is suitable for discharge.
- ° The IV dose cohorts will also have an end-of-infusion PK time point.
- p Spot urine collection.
- q Sample for ADA assessments will be collected prior to administration of the drug. In the event of suspected SAE like hypersensitivity or anaphylaxis, additional samples may be collected for ADA assessments at or near the event.
- r See Section 10.4 for details.
- s Collect 3 lab samples after a suspected hypersensitivity reaction: as soon as possible and at 2 and 8 hours after the suspected reaction (+ 1 hour window for each sample). If the suspected hypersensitivity reaction persists beyond 8 hours, the CRU should contact the Medical Monitor for guidance. Predose samples will only be analyzed for participants with a reported suspected hypersensitivity reaction.

Abbreviations: ADA = antidrug antibody; BMI = body mass index; C5b-9 = terminal complement complex; CRU = clinical research unit;

ECG = electrocardiogram; h = hours; HIV = human immune deficiency virus; I = injection; ICF = informed consent form; IEC = Independent Ethics Committee;

OP = outpatient; min = minutes; PA = pyridoxic acid; PD = pharmacodynamic; PK = pharmacokinetic; PL = pyridoxal; PLP = pyridoxal 5'-phosphate;

PPi = inorganic pyrophosphate; SOI = start of infusion; TEAE = treatment-emergent adverse event; TESAE = treatment-emergent serious adverse event

Table 3: Schedule of Activities – Single Ascending Dose Cohorts (Day 6 through Day 75)

Study Day a	Day 6 post	Day 7 post	Day 8 post	Day 15 post	Day 22 post	Day 29 post	Day 36 post	Day 43 post	Day 75 post I/SOI		
Status (OP or CRU)	I/SOI	I/SOI	I/SOI	I/SOI	I/SOI O	I/SOI P	I/SOI	I/SOI	(EOS/ED b )		
Full physical examination								X			
Brief physical examination			X	X		X					
Vital sign measurements c			X	X		X		X			
12-lead ECG (triplicate) d	X	X	X	X				X			
Chemistry			X	X	X	X	X	X	X		
Hematology			X	X	X	X	X	X	X		
Coagulation			X	X	X	X	X	X	X		
Urinalysis (via dipstick)			X	X	X	X	X	X	X		
Urine pregnancy test e						X					
Serum pregnancy test e								X	X		
PK	X	X	X	X	X	X	X	X	X		
PD (PPi, PLP, PL, and PA)			X	X	X	X	X	X	X		
Immunogenicity samples f						X		X	X		
Urine for calcium, phosphorus, and creatinine g			X	X		X		X	X		
Hypersensitivity reactions h		←Monitor continuously after dose→									
Hypersensitivity reaction laboratory tests (tryptase and	$\leftarrow$ See footnote h $\rightarrow$										
complement C5b-9) i											
Concomitant medications	←Monitor continuously (after ICF is signed at Screening)→										
Adverse event review and evaluation			←Moni	tor continue	ously (after	ICF is sign	ed at Screen	ning)→			

Note: When scheduled at the same timepoint, the triplicate ECG should be performed first, followed by vital sign measurements, and then PK/PD sampling.

- a Permitted windows for study assessments are described in the Windows Allowance Document.
- b EoS procedures will be performed on Day 75. If possible, participants who withdraw/are withdrawn from the study should have an ED visit conducted at the time of discontinuation that includes the EoS assessments. All efforts will be made to contact participants who discontinued early from the study via phone for a safety follow-up call approximately 30 days (4.5 half-lives) after their last dose to assess AEs.
- c Vital signs taken postdose will be performed before the coinciding blood collection, whenever possible.
- d Each ECG will be 12-lead and performed in triplicate sequentially within 5 minutes, at least 1 minute apart after 10 minutes of bedrest in supine position (note, no bedrest is required post ECG). ECGs should not be assessed within 1 hour after any major meal or major meals should be withheld until after ECG assessments.
- e Only female participants of childbearing potential will have a pregnancy testing to confirm the participant is not pregnant.
- f Sample for ADA assessments will be collected prior to administration of the drug. In the event of suspected SAE like hypersensitivity or anaphylaxis, additional samples may be collected for ADA assessments at or near the event.
- g Spot urine collection.

Protocol Amendment 3 ALXN1910-HV-101 27 Jul 2022

Abbreviations: ADA = anti-drug antibody; C5b-9 = terminal complement complex; CRU = clinical research unit; ECG = electrocardiogram; ED = early discontinuation; EOS = end of study; h = hours; I = injection; ICF = informed consent form; OP = outpatient; PA = pyridoxic acid; PD = pharmacodynamic; PK = pharmacokinetic; PL = pyridoxal; PLP = pyridoxal 5'-phosphate; PPi = inorganic pyrophosphate; SOI = start of infusion; TEAE = treatment-emergent adverse event; TESAE = treatment-emergent serious adverse event

<sup>h See Section 10.4 for details.

<sup>1 If the participant is in the clinic, collect the first sample as soon as possible (preferred) or within 1 hour of the suspected hypersensitivity reaction, and 2 additional samples at 2 and 8 hours after the suspected hypersensitivity reaction (+ 1 hour window for each sample). If the participant is not in the clinic, these samples do not need to be collected and suspected hypersensitivity reactions will be reported as TEAEs/TESAEs only. If the suspected hypersensitivity reaction persists beyond 8 hours, the CRU should contact the Medical Monitor for guidance.

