# 4.5. Duration of Treatment and End of Study Definition

[figure not shown]
Following a Screening Period of up to 28 days, there will be a Dosing and Follow up Period (single dose on Day 1 through the EOS Visit) of approximately 74 days.

Based on data from preclinical models, the half-life of ALXN1910 is expected to be approximately 7 days in healthy adult participants; therefore, the end of study visit is planned on Day 75, representing approximately 10 half-lives after initial study intervention administration. The total study duration per participant is approximately 103 days. An overview of the study visits is present in Figure 2.

A participant is considered to have completed the study if they complete all visits of the study including the last scheduled visit specified in the SoA (Section 1.3).

The end of the study is defined as the date the last participant completes the last visit (as specified in the SoA [Section 1.3]).

Figure 2: Overview of Study Visits

Abbreviation: D = day

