# 7.3. Participant Discontinuation/Withdrawal from the Study

- All efforts should be made to ensure participants are willing to comply with study participation prior to conducting the screening procedures.
- The study staff should notify Alexion and their site monitor of all study withdrawals as soon as possible. The reason for participant discontinuation must be recorded in the source documents and eCRF.
- A participant may withdraw from the study at any time at their own request or may be withdrawn at any time at the discretion of the Investigator for safety, behavioral, compliance, or administrative reasons. This activity is expected to be uncommon.
- At the time of discontinuing from the study, an early discontinuation visit should be conducted that includes the EOS assessments shown in the SoA, if possible (Section 1.3).
- All efforts will be made to contact participants who withdraw/are withdrawn from the study via phone for a safety follow-up call approximately 30 days (4.5 half-lives) after their dose to assess AEs.

- The first participant in each cohort to withdraw/be withdrawn from the study prior to completion of the EOS assessments may not be replaced; subsequent participants in that cohort to withdraw/be withdrawn before EOS completion will be replaced.
- If the participant withdraws consent for disclosure of future information, Alexion may retain and continue to use any data collected before such a withdrawal of consent.
- If a participant withdraws from the study, the participant may request destruction of any samples taken and not tested, and the Investigator must document this in the site study records.

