## 8.3.1. Time Period and Frequency for Collecting AE and SAE Information

- All AEs and SAEs will be collected from the signing of the ICF until the EOS visit on Day 75 as specified in the SoA (Section 1.3).
- All SAEs will be recorded and reported to Alexion immediately and under no circumstance should this exceed 24 hours of the Investigator's awareness, as indicated in Section 10.3. The Investigator will submit any updated SAE data to Alexion within 24 hours of the date the investigational site became aware of the event.
- Investigators are not obligated to actively seek AE or SAE data after conclusion of the study participation. However, if the Investigator learns of any SAE, including a death, at any time after a participant has been discharged from the study, and they

consider the event to be reasonably related to the study intervention or study participation, the Investigator must promptly notify Alexion.

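### Participants who leave early have no scheduled adverse event contact after about Day 31 or a later discontinuation visit, although adverse events are to be collected to Day 75

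*Protocol*

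**What the plan says.** Protocol Section 4.5 describes a "Dosing and Follow up Period (single dose on Day 1 through the EOS Visit) of approximately 74 days". It gives the reason for the last visit from the pharmacokinetics: "the half-life of ALXN1910 is expected to be approximately 7 days in healthy adult participants", and so "the end of study visit is planned on Day 75, representing approximately 10 half-lives after initial study intervention administration". Section 8.3.1 sets the safety window: "All AEs and SAEs will be collected from the signing of the ICF until the EOS visit on Day 75".

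Two contacts are planned for participants who leave early. Section 7.3 says that "an early discontinuation visit should be conducted that includes the EOS assessments shown in the SoA, if possible". It also plans a "safety follow-up call approximately 30 days (4.5 half-lives) after their dose to assess AEs". Table 3 footnote b in Section 1.3 gives the same timing ("safety follow-up call approximately 30 days (4.5 half-lives) after their last dose to assess AEs"), and so does the matching footnote in SAP Section 6.1. Neither document schedules a later AE contact for leavers, or says what applies when someone leaves after the call date has passed. Section 8.3.1 adds that investigators need not actively look for events once participation has ended.

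**The concern.** The call is tied to the dose and not to the date of leaving or the end of the AE window. A participant who leaves on Day 6 is due a call at about Day 31 and nothing after that. One who leaves at the Day 36 or Day 43 visit is already past the call date, so the discontinuation visit closes scheduled ascertainment.

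The primary endpoint is the incidence of treatment-emergent AEs and SAEs. If leavers are observed for less time than completers but counted in the same denominator, their late events can be missed and incidence comes out too low. This is a first-in-human study, and Table 4 of the protocol names immunogenicity as a potential risk. Post-dose antidrug antibody samples are taken on Days 29, 43 and 75, so two of the three fall after the call. Protocol Section 9.4.2.3 foresees relating antibody response to serious and severe events, which works best when events are sought over the same period.

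**Working it through.** **Inputs.** One dose on Day 1, about 74 days of follow-up and a half-life of about 7 days (Section 4.5). Call at about 30 days, stated as 4.5 half-lives (Table 3 footnote b; Section 7.3; SAP 6.1). AE window to Day 75 (Section 8.3.1). Six active and two placebo participants per cohort, 36 and 12 overall (Section 4.1).

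**The plan's own figures.** 30 / 7 = 4.29 half-lives, which is 4.5 to the nearest half. In reverse, 30 / 4.5 = 6.7 days, or about 7. For Day 75, 74 / 7 = 10.6 against a stated value of about 10. All of these are labelled approximate and agree within rounding.

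**Day of the call.** 1 + 30 = Day 31. If 4.5 half-lives is taken literally, 4.5 × 7 = 31.5 days, which is Day 32 to 33.

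**Leaving before the call.** Share of the post-dose window with scheduled ascertainment, assuming the call is made and answered:
- 30 / 74 = 40.5%, leaving 74 − 30 = 44 days uncovered;
- at 31.5 days, 31.5 / 74 = 42.6%, leaving 42.5 days.

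**Leaving after the call, on Day d**, with the discontinuation visit held. The share is (d − 1) / 74 and the uncovered period is 75 − d days:
- Day 36: 35 / 74 = 47.3%, 39 days uncovered;
- Day 43: 42 / 74 = 56.8%, 32 days uncovered.

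**Counting from consent instead of dosing.** With s pre-dose days, an early leaver's share is (s + 30) / (s + 74): 42% at s = 2, 50% at s = 14, 57% at s = 28. The post-dose share is the relevant one for treatment-emergent events.

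**How the analysis treats a leaver.** SAP Section 4.4.1 keeps every dosed participant in the Safety Set. SAP 4.2.6 uses N as the denominator for percentages. SAP 4.16 imputes nothing except partial dates. SAP 4.13.1 plans participant counts, percentages and event counts, with no adjustment for time observed. A leaver with no event by Day 31 is thus counted in the same way as a completer with no event by Day 75.

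**Size of one missed event.** Participants are counted once per category, so overall incidence changes only if the leaver had no other treatment-emergent event. In that case:
- one active cohort: 1 / 6 = 16.7 percentage points;
- all active participants: 1 / 36 = 2.8 points;
- pooled placebo: 1 / 12 = 8.3 points.

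**Number of leavers.** The documents give none. At an assumed 0 to 10% withdrawal, 0 to 0.10 × 48 = 4.8 participants, active and placebo together, would leave early. Only some of them would have a late event that goes unreported.

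**The case against.** The two rules can be read together without contradiction. The last column of Table 3 serves both the end-of-study and the early-discontinuation visit, so for a leaver the discontinuation visit can stand in for Day 75. The call is then a minimum for those who go sooner, and someone leaving on Day 43 has already passed that minimum. This reading is fair and answers a charge of formal inconsistency. It does not change the effect on the endpoint, because the leaver is still counted as if observed for the full period.

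Other provisions narrow the gap, and they stand:
- Reported SAEs are followed until they resolve or stabilise (Section 8.3.3).
- The investigator stays responsible for following serious events and related events (Section 8.3).
- A related SAE that the investigator hears of later must still be notified (Section 8.3.1).
- Participants whose administration is stopped for a severe reaction are told to attend every visit (Section 10.4).
- Withdrawal is expected to be uncommon, and second and later leavers in a cohort are replaced (Section 7.3). The dosed leaver nevertheless remains in the Safety Set.
- A leaver who attends the discontinuation visit has an antibody sample there. No passage reports late immune events, and the stated reason in Amendment 3 for bringing everyone back on Day 75 is blinding.

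A reader might infer more than the text supports. It would be wrong to say that leavers get no further contact: what is missing is scheduled AE contact. The period after the call is 44 of 74 days (59%), but that is a share of calendar days, not of withdrawals or participants. The 4.5 half-lives is not an error, since it is a rounding of two approximate figures.

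**Conclusion.** The point holds as a limited gap in ascertainment. Leavers before about Day 31 have scheduled AE contact over about 30 of 74 post-dose days; for later leavers it ends at a discontinuation visit that may not take place. Late events that nobody reports could be missed, and incidence of treatment-emergent events could be biased low.

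The bias is possible, not shown. It requires that someone leaves early, has a late event, and does not report it. The 16.7 points for a cohort of six active participants is a ceiling and should not be read as the expected effect. A missed event in a placebo leaver would lower the placebo figure instead, so the direction of any error in the comparison with placebo is not fixed. The number of leavers is unknown and probably small. This is a cheap improvement and does not call the design into question.

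**What to change.** Reconcile Table 3 footnote b, Section 7.3 and the SAP Section 6.1 footnote with the Day 75 window in Section 8.3.1. Keep the existing call. Add a telephone contact at Day 75, solely to collect AE data, for every participant who left early and has not refused contact.

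The cost is a wording change in the protocol and SAP and one call per leaver, with no added visit or sample. Some leavers will not answer, so the gap would be reduced but not fully closed.
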